8.6.4 Prior and concomitant medication

All medications will be coded using the WHO-DD drug codes of the most recent version (WHO-DD Global B3 Sep 2019, or later version) resulting in ATC codes indicating therapeutic classification.

Prior and concomitant medications will be defined using start and stop dates recorded, relative to the first and last IMP administration dates.

A **prior medication** will be defined as any therapy taken prior up to (but not including) the start date of first IMP administration.

A **concomitant medication** will be defined as any medication either ongoing at the start date of first IMP administration or with a start date on or after the first IMP administration date up to (but not including) the Safety FU-D30 or Safety FU-D90 visit as appropriate.

The number and percentage of patients taking prior medication or concomitant medications will be summarized by ATC therapeutic class (ATC level 2), ATC pharmacological class (ATC level 3), and chemical substance (ATC level 4) for each treatment group based on the mITT set.

A listing of prior and concomitant medications will be provided for the ITT set.

In addition, a listing of further antineoplastic therapies after discontinuation of IMPs, as collected in the eCRF, will be generated.

8.6.5 Other Procedures

Concomitant cancer radiotherapy:

During the course of the trial concomitant new cancer radiotherapies within 28 days prior to start of first IMP administration up to (but not including) the Safety FU-D30 or Safety FU-D90 Visit as appropriate will be reported.

A summary table presenting the number and percentage of patients with any concomitant cancer radiotherapy, including information of site will be summarized by treatment group for the mITT set. All data will be listed for the ITT set.

Concomitant Procedures and Non-Drug Therapies:

During the course of the trial concomitant procedures/non-drug therapies, e.g. invasive procedures / surgery, may take place and will be documented on the eCRF page "Procedures / Non-Drug Therapies". Data will be reported within 28 days prior to start of the first administration of IMP up to (but not including) the Safety FU-D30 or Safety FU-D90 Visit as appropriate will be reported. Procedures and Non-Drug Therapies will be coded using MedDRA (version 22.1 or later version).

The number and percentages of patients with any concomitant procedures/non-drug therapies will be summarized by SOC and PT for each treatment group for the mITT set.

All data will be listed for the ITT set.

8.6.6 Medical history

Medical history data will be coded using MedDRA (version 22.1 or later version). The number and percentage of patients with a medical history (prior medical history and concomitant diseases) will be summarized by SOC and PT. This summary will be done by treatment group for patients in the mITT set.

Medical history terms with ongoing ticked "No" will be considered as prior medical history, with ongoing ticked "Yes" as concomitant diseases.

A listing of medical history data will be provided for the ITT set.

8.7 Efficacy analyses

8.7.1 Primary analysis

8.7.1.1 Primary Efficacy Endpoint

Objective Response Rate

For Part 2, Arms 1A and 1B, ORR is defined as primary efficacy endpoint. The primary analysis will be performed using the mITT set.

The ORR is defined as the number of patients with CR or PR as best objective response per PCWG3 divided by the number of patients in the mITT set. Patients not meeting the criteria for CR or PR, including those without any post-baseline response assessments, will be considered as non-responders. The ORR will be summarized with absolute and relative frequencies along with two-sided 95% Clopper-Pearson CIs by treatment group.

For each Part 2 Arm 1A and 1B the null hypothesis (see Section 4) that the true response rate is 5% will be tested against a one-sided alternative (i.e. H_0 : ORR=5% versus H_1 : ORR >5%). There will be no formal comparison between treatment groups.

BOR (all categories) based on PCWG3 will be summarized with absolute and relative frequencies.

Further, the BOR (all categories) based on Radiological Soft Tissue Evaluation will be summarized with absolute and relative frequencies.

For Part 1, ORR is defined as secondary endpoint as best objective response and will be analyzed descriptively.

Tumor response assessment including overall response, BOR and clinical progression as documented in the eCRF will be listed. In addition, listings including all tumor assessments per PCWG3 (target lesion, non-target lesion, new lesion) will be generated.

Subgroup analyses of the primary efficacy endpoint will be performed for the mITT set.

Sensitivity analysis

For the primary endpoint ORR, sensitivity analyses will be performed using the ITT set and the PP set.

8.7.2 Supplementary analyses

Not applicable.

8.7.3 Secondary analyses

8.7.3.1 Secondary efficacy endpoints

Prostate-specific antigen decline

PSA will be collected for all patients in Part 1 and Part 2 at several visits during the course of the trial (see SoA in Section 13.6 for more details). PSA values will be provided by a central laboratory and reported by the investigator in the database. For the analyses, it

was agreed to use the PSA measurements as provided by the investigator together with the PSA response per PCWG3 criteria as reported in the database.

PSA decline calculated as percentage change compared to baseline will be summarized using descriptive summary statistics for each visit by treatment group.

PSA decline of 0 to 25%, > 25% to 50%, and > 50% compared with baseline and PSA decline of <50% versus ≥50% compared to baseline will be summarized with absolute and relative frequencies (n and %) of patients by visit and treatment group for the mITT set.

Bar charts for PSA decline compared to baseline in the above defined categories by visit will be generated for the mITT set.

Waterfall plots for maximum PSA decline from baseline per patient will be generated.

For the derivation of maximum decline from baseline only measurements which were reported ≥ 4 weeks after treatment start and prior to or at the EoT visit and prior to or at the start date of the subsequent anti-cancer therapy to be considered. Only PSA measurements corresponding to a confirmed PSA response (see Section 8.2 for the definition of confirmed PSA response) or reported after a confirmed PSA response have to be considered in the derivation of maximum PSA decline (an initial PSA response will confirm all subsequent PSA responses of the same response value, as long as there is not a better or worse response between them).

PSA response per PCWG3 criteria (as reported by the investigator) will be summarized with absolute and relative frequencies (n and %) of patients by visit and treatment group for the mITT set.

Best overall PSA response, ORR and Clinical Benefit Rate (CBR) per PCWG3 criteria will be summarized for the mITT set.

Sensitivity analyses for PSA decline will be performed using the ITT set and the PP set depending on the number of patients excluded.

Prostate-specific antigen doubling time

The number and percentage of patients per PSADT under-treatment on C4D1 and D1 of every fourth subsequent cycle (e.g., C8D1, C12D1, etc.) in Part 1 and Part 2 Arm 1A and 1B, or on C4D1, C8D1, and EoT in Part 2 Arms 2 and 3 compared with baseline. For more details for the calculation of PSADT, see Section 8.2.

The following categorization of PSADT should be reported: 0 - 3 months, >3 – 6 months, >6 – 9 months, >9 – 12 months, >12 – 18 months, >18 – 24 months, >24 months.

Sensitivity analyses will be performed using the ITT set and the PP set depending on the number of patients excluded.

Objective Response Rate for Part 1

For Part 1, ORR is defined as secondary efficacy endpoint as best objective response per PCWG3 and will be analyzed descriptively for the mITT set. For more details, see Section 8.7.1.1.

Tumor assessment post-treatment compared to baseline for Part 2, Arm 2 and Arm 3

Tumor measurements using mpMRI or, if tumor measurement is not feasible with a mpMRI, imaging according to local practice (e.g. CT or MRI), should be performed at the following time points:

- During the screening period (within 28 days before C1D1 (baseline))
- Prior to surgery (i.e. at the end of C8/EoT Visit)

Tumor response will be assessed based on Radiological Soft Tissue Evaluation at both time points. Number of patients in each category and ORR will be summarized with absolute and relative frequencies along with two-sided 95% Clopper-Person CIs by treatment group for the mITT set.

Tumor response assessment including overall response, best overall response and clinical progression as documented in the eCRF will be listed. In addition, listings including all tumor assessments per PCWG3 (target lesion, non-target lesion, new lesion) will be generated.

Sensitivity analyses will be performed using the ITT set and the PP set depending on the number of patients excluded.

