#### 2. Introduction

#### 2.1. Background

#### 2.1.1. Overview of the Disease(s)

Prostate cancer is the second most common malignant neoplasm in men worldwide, with an estimated 1,276,106 incidences and 358,989 deaths in 2018. The incidence of prostate cancer has increased over the past 20 years (largely due to the wide availability of prostate-specific antigen [PSA] testing), and currently prostate cancer is the most frequently diagnosed cancer among men worldwide (13.5%); in Germany (18.9%), the United Kingdom (UK; 23.6%) and in the United States of America (USA; 18.5%). Although mortality rates do not follow those of incidence, prostate cancer is still the fifth cause of cancer-related death worldwide (6.7%) and the leading cause of cancer deaths among men in 46 less-developed countries.

PSA is a protein exclusively generated in prostate cells and high levels of PSA in the blood are often an indication of prostate cancer. Blood levels of PSA are commonly used to gauge the success of treatment, and the presence of recurrence. The risk of clinically significant prostate cancer is related to age, ethnicity, family history, PSA level, free/total PSA ratio, and findings from digital rectal examination. PSA screening for prostate cancer reduces prostate cancer mortality by allowing early diagnosis of the disease and implementation of curative treatments in many patients.

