## 2.1.3. Non-Investigational Medicinal Products (NIMP)

#### 2.1.3.1. Androgen-deprivation therapy followed by radical prostatectomy

Patients should be eligible for up to 6 months of ADT followed by radical prostatectomy. The sponsor will provide goserelin acetate if requested by the investigational site, however other types of ADT are allowed according to local clinical practice. In such cases, the investigational site will organize and reimburse the ADT of choice. The ADT can be interrupted any time prior to the radical prostatectomy and/or other clinically indicated treatment or intervention based on the investigator's decision.

Goserelin acetate (e.g., Zoladex® LA 10.8 mg implant): The luteinizing hormone-releasing hormone (LHRH) agonist Goserelin acetate, (synonym: D-Ser(But)6Azgly10-LHRH) is a synthetic analogue of the naturally occurring gonadotropin releasing hormone. Goserelin acetate 10.8 mg is indicated in the treatment of metastatic or locally advanced prostate cancer and as adjuvant treatment to radical prostatectomy or radiotherapy, and as neoadjuvant treatment prior to radiotherapy in patients with high-risk localized or locally advanced prostate cancer. Goserelin acetate is injected subcutaneously (SC) into the anterior abdominal wall every 12 weeks (Q12W). On chronic administration, goserelin acetate results in inhibition of pituitary luteinizing hormone secretion leading to a fall in serum testosterone concentrations in males and serum estradiol concentrations in females. This effect is reversible on discontinuation of therapy. Initially, goserelin acetate, like other LHRH agonists, may transiently increase serum testosterone concentration in men and serum estradiol concentration in women. In men, by around 21 days after the first depot injection, testosterone concentrations have fallen to within

CONFIDENTIAL Page 38 of 122

the castrate range and remain suppressed with treatment Q12W. This inhibition leads to prostate tumor regression and symptomatic improvement in the majority of patients.

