Part 1 (dose titration) of the PRO-MERIT trial has been performed in the UK and Hungary and enrollment has been completed with 9 patients dosed. The SRC reviewed the available safety data for patients in Part 1 on 17 MAY 2021. The safety profile observed indicates that BNT112 a tolerable drug product with a manageable safety profile at the defined dose range µg) using the intra-patient step-up dose titration scheme. Observed AEs considered related to the IMP (including pyrexia, flu-like symptoms, hypertension, nausea, chills or headache), are in line with the innate immune activation by RNA-LPX, are transient in nature and manageable by analgesics, antipyretics or fluids at recommended and usual doses. The recommendation was to continue to Part 2 at the selected REDR ( to QCI µg) using the intra-patient step-up dose titration scheme. The annual review of safety data for the IB update occurred on 20 MAY 2021 (data extraction date) and included safety data from patients in Part 1 as well as Part 2. Neither the safety profile nor the benefit-risk assessment were changed.

**Cemiplimab** is given at a dose of mg as an IV infusion over 30 minutes every 3 weeks.

Goserelin acetate is administered at a dose of 10.8 mg as an SC injection into the anterior abdominal wall Q12W, according to the current SmPC (e.g., Zoladex® LA 10.8 mg implant). In order to facilitate interpretation of toxicities with suspected relationship to the IMP, goserelin acetate is to be administered anytime within 7 days prior to the start of BNT112 treatment. In case another ADT is used, it is to be administered in line with the current prescribing information valid in a given country.

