# Non-investigational medicinal product (NIMP):

#### Part 2 Arms 2 and 3 (LPC)

ADT, e.g., Goserelin acetate subcutaneous (SC) injection at a dose of 10.8 mg every 12 weeks or other ADT according the current prescribing information valid in a given country.

Product:	Goserelin acetate (Zoladex® LA 10.8 mg implant)
Composition:	Goserelin acetate (equivalent to 10.8 mg goserelin)
Administration:	SC
Dosage regimen:	One 10.8 mg depot injection given into the anterior abdominal wall every 12 weeks (Q12W)
Duration of treatment:	Two injections (C1D1 and C5D1); treatment will last until unacceptable toxicity or disease progression, or up to C8

CONFIDENTIAL Page 60 of 122

Figure 6-1: Treatment Administration – Part 1 and Part 2

Part 1

Dose Titration®

	C1				C2		C3 →		
Day	1	8	15	1	8	15	1	8	15
			BN	T112 \$					
ССІ µg IV	х								
μg IV		х							
CCI μg IV			х						
dose*				Х	Х	Х	Х	$\rightarrow$	Q3W

Part 2

Arm 1b% (BNT112 monotherapy in mCRPC)
Arm 3# (BNT112 monotherapy in LPC)

Part 2

Arm 1a (BNT112 + cemiplimab in mCRPC)

Arm 2# (BNT112 + cemiplimab in LPC)

	C1				C2		C3 →		
Day	1	8	15	1	8	15	1	8	15
	BNT112 								
ccι μg IV	х								
CCI µg IV		×							
CCI ug IV			х	х	х	х	х	$\rightarrow$	Q3W

	C1				C2		C3 →			
Day	1	8	15	1	8	15	1	8	15	
BNT112 										
CCI ug IV	х									
μg IV		х								
CCI μg IV			х	х	х	х	х	$\rightarrow$	Q3W	
Cemiplimab										
CCI mg IV Q3W	х			х			х	$\rightarrow$	Q3W	

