8.2 Key definitions

Date/time of first administration of IMP (W_pro1 or Cemiplimab):

Is defined as first administration date/time of IMP (W_pro1 or cemiplimab), whichever was administered first.

Baseline Definition:

Baseline is defined as last available value prior to or on the date/time of first administration of IMP (W_pro1 or cemiplimab, whichever was administered first). Unscheduled measurements prior to first administration of IMP will be considered in the calculation of the baseline values. In the case that date/time of first administration of IMP is missing (i.e.,

for randomized not treated patients) the date/time of randomization will be used for the definition of baseline values.

Cemiplimab Baseline – Baseline definition for Arm 1B patients who switch to cemiplimab monotherapy:

Cemiplimab Baseline is defined as last available value prior to or on the date/time of first administration of cemiplimab.

In case no time of the assessment is reported, measurements at the same date as first administration of cemiplimab will be considered as baseline.

Change and percent change from baseline:

Change from baseline will be calculated as follows:

- Change from baseline = post-baseline assessment value – baseline assessment value.
- Percent change from baseline = (post-baseline assessment value – baseline assessment value) / baseline assessment value * 100.

Age (in years) at date of informed consent:

Age is derived in the database based on the collected Year of birth as follows:

Age = ICF Date – (01July + Year of birth) / 365.25.

Age as derived in the database will be used for all analyses.

Body mass index (BMI):

BMI will be calculated as follows:

$$\text{BMI} \left(\frac{\text{kg}}{\text{m}^2} \right) = \frac{\text{Weight (kg)}}{\text{Height(m)}^2}$$

Duration:

Duration will be calculated as follows:

- Duration (days) = last observation date – first observation date + 1

For conversion of days to months or years the following rules will be applied:

- 1 month = 30.4375 days
- 1 year = 365.25 days

Time from first diagnosis to enrollment (in months):

Date of initial diagnosis is collected in Month/Year. Missing day will be replaced with the first day of the month. In case month is not reported, missing month will be replaced with July.

Time from first diagnosis to enrollment (months) will be calculated as:

(ICF date – imputed date of initial diagnosis) / 30.4375

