8.7.5 Further efficacy analyses

Survival status and biochemical recurrence

Survival status will be assessed at month 6 and month 12, beginning from the day of the last IMP dose and continues until the patient dies or withdrawal from the trial.

Disease status (CR, PR, SD, PD, Unknown) will be collected for all patients in Part 1 and Part 2 on the survival follow-up CRF page and will be summarized with absolute and relative frequencies at time points as collected during the survival follow-up reporting period.

Biochemical recurrence after radical prostatectomy based on the post-treatment PSA levels at Efficacy FU Month 6 and FU Month 12 will be summarized for patients in Arms 2 and 3.

For LPC patients (Arm 2 and Arm 3) the time (in days) from treatment start to post treatment prostatectomy will be reported.

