	14.2.1.1.1.1	Objective Response Rate (ORR) based on PCWG3 by age category	mITT set	
	14.2.1.1.1.1a	Objective Response Rate (ORR) based on PCWG3 by age category, SAS output	mITT set	
	14.2.1.1.1.2	Objective Response Rate (ORR) based on PCWG3 by subgroup 2	mITT set	
	14.2.1.1.1.2a	Objective Response Rate (ORR) based on PCWG3 by subgroup 2, SAS output	mITT set	
	14.2.1.1.4	Objective Response Rate (ORR) based on Radiological Soft Tissue Evaluation per Investigator	mITT set	Yes
	14.2.1.1.5	Clinical Progression	mITT set	Yes
14.2.2		Secondary Efficacy Parameters		
14.2.2.1		Secondary Efficacy Parameter 1: PSA decline		
	14.2.2.1.1	PSA decline for each visit compared to baseline (including all PSA data as reported)	mITT set	
	14.2.2.1.2	PSA decline for each visit compared to baseline (including all PSA data as reported) (optional)	ITT set	

Header	Table Number	Name	Analysis Set	Interim Analysis
	14.2.2.1.3	PSA decline for each visit compared to baseline (including all PSA data as reported) (optional)	PP set	
	14.2.2.2	Best PSA decline compared to baseline	MITT set	Yes
Figure	14.2.2.2.1	PSA decline (Categorization 1): Bar Chart for each visit compared to baseline (including all PSA data as reported)– MITT set – mCRPC patients	MITT set	
Figure	14.2.2.2.2	PSA decline (Categorization 1): Bar Chart for each visit compared to baseline (including all PSA data as reported)– MITT set – LPC patients	MITT set	
Figure	14.2.2.2.3	PSA decline (Categorization 2): Bar Chart for each visit compared to baseline (including all PSA data as reported)– MITT set – mCRPC patients	MITT set	
Figure	14.2.2.2.4	PSA decline (Categorization 2): Bar Chart for each visit compared to baseline (including all PSA data as reported)– MITT set – LPC patients	MITT set	
	14.2.2.3.1	PSA decline: Summary by visit and percentage change from baseline (including all PSA data as reported)	MITT set	
	14.2.2.3.2	PSA decline: Summary by visit and percentage change from baseline (including all PSA data as reported) (optional)	ITT set	
	14.2.2.3.3	PSA decline: Summary by visit and percentage change from baseline (including all PSA data as reported) (optional)	PP set	
Figure	14.2.2.4.1	PSA decline: Waterfall plot of maximum decline from baseline – MITT set – mCRPC patients	MITT set	
Figure	14.2.2.4.2	PSA decline: Waterfall plot of maximum decline from baseline – MITT set – LPC patients	MITT set	

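### In LPC Arms 2 and 3, the by-visit PSA displays and PSA response have no cut-off at radical prostatectomy, so post-surgery values enter a secondary endpoint

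*SAP*

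**What the plan says.** PSA decline is a secondary endpoint meant to show anti-tumor activity, and it applies to all arms (SAP Table 3-1). SAP 8.7.3.1 states: "PSA decline calculated as percentage change compared to baseline will be summarized using descriptive summary statistics for each visit by treatment group". The same section tabulates the decline categories and the investigator-reported PSA response by visit. In SAP 11.1.1 the table title reads "PSA decline for each visit compared to baseline (including all PSA data as reported"; the percent-change tables, the separate LPC bar charts and the PSA-response tables carry the same qualifier. SAP 8.1 brings scheduled visits into by-visit tables.

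In the LPC schedule of activities the PSA row has marks that fit EoT, Safety FU, Month 6, Month 12 and a Surgery column. A footnote places the last of these six weeks (±1 week) after prostatectomy. SAP 8.7.5 uses some of these values for another purpose: "Biochemical recurrence after radical prostatectomy based on the post-treatment PSA levels at Efficacy FU Month 6 and FU Month 12". Protocol 8.3.3 schedules surgery after the EoT visit, and Protocol 7.1 allows it earlier at the investigator's discretion.

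**The concern.** Protocol 2.1.1 says "PSA is a protein exclusively generated in prostate cells". Once the prostate is removed, a fall in PSA is the expected result of surgery and says little about the study drugs. Under the plan as written, those falls are counted in the same decline categories, and under the same endpoint heading, as on-treatment values.

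Best overall PSA response is more exposed than the by-visit rows because it reduces all visits to one result per patient. If prostatectomy is not treated as a subsequent anti-cancer therapy, a post-surgery PSA can create a response or confirm an earlier one, and the response rate in Table 14.2.2.5.4 rises for a reason unrelated to treatment.

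**Working it through.** The plan states no figure to reproduce here. The check compares the cut-off rules, places the visits on a timeline, and illustrates the size.

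**1. Last PSA value admitted, by output**

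| Output | Last value admitted | Source |
|---|---|---|
| By-visit decline and percent change (14.2.2.1.x, 14.2.2.3.x), LPC bar charts (14.2.2.2.2, 14.2.2.2.4), PSA response by visit (14.2.2.5.1 to 14.2.2.5.3) | No limit stated | SAP 8.7.3.1, 11.1.1 |
| Best overall PSA response, PR and SD confirmation, Table 14.2.2.5.4 | Start of next anti-cancer therapy (PD: 14 days more) | SAP 8.2 |
| Maximum decline (waterfall plots) | EoT and start of next anti-cancer therapy | SAP 8.7.3.1 |
| PSA doubling time | EoT and start of next anti-cancer therapy | SAP 8.2 |

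An EoT limit was applied to the last two outputs and not to the first two.

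**2. Timeline for a patient completing eight cycles** (C1D1 = day 1, 21-day cycles, 1 month = 30.4375 days)

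- C8D1, last dose: 1 + 7 × 21 = day 148.
- EoT, up to 21 days later: day 169 (or combined with the D30 visit).
- D30 with its +7-day window: days 178 to 185. D90 (Arm 2): days 238 to 245.
- Month 6: 148 + 183 = about day 331. Month 12: 148 + 365 = about day 513.

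The six-week draw is post-surgery by definition. Months 6 and 12 are post-surgery if the operation follows EoT as planned. D30 and D90 may fall on either side, because no surgery date is fixed.

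**3. Size of the decline after surgery**

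Decline (%) = 100 × (1 − post / baseline). The documents give no post-surgery PSA values, so these are assumptions: baseline 2 to 40 ng/mL, post-surgery 0.01 to 0.5 ng/mL.

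- Smallest: 100 × (1 − 0.5/2) = 75%.
- Largest: 100 × (1 − 0.01/40) = 99.975%.
- Middle example, 20 falling to 0.2: 99%.

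Over that whole range every value falls in both the >50% and the ≥50% category. With 20 patients in an arm, all operated on and sampled, the row would read 20/20 with no treatment effect.

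**4. Route into best overall PSA response**

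A PSA PR needs a later PR at least 20 days on. Take an Arm 3 patient with no PSA response through D30, operated on at day 190 (assumed date). The six-week draw is at 190 + 42 = day 232, and Month 6 is at about day 331, a gap of 99 days. With both visit windows used against it, the gap is (331 − 14) − (232 + 7) = 78 days. If the investigator records PR at both draws and surgery is not counted as subsequent therapy, the patient becomes a confirmed PSA responder on two post-surgery values. The waterfall plots admit only values tied to or following a confirmed response, so a post-surgery confirmation could also let a pre-EoT value into them.

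**The case against.** The by-visit tables do not pool visits, so follow-up values cannot change the C1 to C8 or EoT rows, which normally precede surgery. The follow-up rows are labelled as such, the endpoint is descriptive, and no LPC hypothesis is tested. All of that stands and limits the problem. It does not cover best overall PSA response, which does combine visits.

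On that output, a footnote to the LPC schedule mentions surgical procedures among the non-drug anti-cancer therapies recorded after IMP stops, which suggests that prostatectomy would trigger the existing limit. But the footnote is a data-collection note, does not name the planned operation, and is not carried into SAP 8.2. It would also leave the by-visit outputs without a limit.

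Three stronger readings are tempting, and the documents do not support them:

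- *The LPC PSA results show only ADT and surgery.* Rows up to EoT reflect ADT plus BNT112, with or without cemiplimab. Protocol 2.1.3.1 says of androgen suppression: "This inhibition leads to prostate tumor regression and symptomatic improvement in the majority of patients". BNT112 therefore cannot be separated out, but that does not show it has no activity. The lack of an ADT-alone arm is a disclosed design feature that no analysis rule removes.
- *The baseline should move to before ADT.* SAP 8.2 states: "Baseline is defined as last available value prior to or on the date/time of first administration of IMP". ADT is not IMP, so baseline can follow its start. But the protocol puts castrate testosterone at around 21 days after the first goserelin depot, that is, study day 15 (ADT seven days before C1D1) to day 22 (ADT on C1D1). Nearly all of the fall already lies after the present baseline, and a pre-ADT baseline would put the whole ADT effect inside the decline.
- *The D90 visit, held for Arm 2 only, biases the comparison.* In a by-visit table that row alters no other row.

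**Conclusion.** The gap is real and confined to Arms 2 and 3. The by-visit PSA decline and PSA-response tables, the LPC bar charts, and best overall PSA response with its confirmation rule have no cut-off at prostatectomy. Post-surgery rows, and any response created or confirmed by a post-surgery value, would reflect removal of the prostate. On the assumed PSA values the top category is filled completely at those visits. The number of patients affected in best overall PSA response cannot be derived from the documents. It depends on how prostatectomy is coded and on whether investigators record PSA response after surgery.

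Rows up to EoT, maximum decline and PSA doubling time are normally unaffected, apart from an operation before the EoT visit and the confirmation route above. The mCRPC arms are not touched.

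**What to change.** In SAP 8.2 and 8.7.3.1, for Arms 2 and 3, restrict Tables 14.2.2.1.x, 14.2.2.3.x and 14.2.2.5.x, the LPC bar charts, best overall PSA response and PR/SD confirmation to PSA values up to EoT or the day before prostatectomy, whichever is earlier. Report later values only under biochemical recurrence (Table 14.2.5.1.2). SAP 8.7.5 names only Months 6 and 12, so add the six-week value there if it is to be reported.

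The cost is a date filter and a few sentences. The surgery date is already collected (Protocol 8.3.3). SAP 8.2 imputes a missing day of surgery as the first of the month, which could drop a valid pre-surgery value, so incomplete dates should be queried. No value is lost, because the listings keep them all.

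Separately, and not needed for this fix:

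- The statements on first ADT timing must be reconciled. Protocol 4.4 says "goserelin acetate is to be administered anytime within 7 days prior to the start of BNT112 treatment", the treatment description in Protocol Section 6 says "Two injections (C1D1 and C5D1", and the synopsis and SAP 3.2 give a third wording.
- List the ADT date against the baseline PSA date.
- Describe LPC PSA decline as the result of ADT plus BNT112 with or without cemiplimab.
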